3 IDENTIFICATION AND DESCRIPTION OF THE INVESTIGATIONAL DEVICE

3.1 Summary Description of VR101

VR101 is a clear, flexible, torus-shaped lubricating intravaginal ring (IVR); see Figure 2, Device Image, and Figure 3, VR101 Schematic Drawing). VR101 is manufactured from hollow tubing formed from Excipient Grade Thermoplastic Urethane Pathway® Polymer PY-PT42DE35 (identical to Tecophilic® HP-60D-35, Lubrizol Advanced Materials, Cleveland, OH) by hot-melt extrusion.

[figure not shown]

Figure 2. Top View of VR101

[figure not shown]

Figure 3. VR101 Manufacturing Drawing with Specifications

The VR101 manufacturing process consists of extruding tubing from Excipient Grade Thermoplastic Urethane Pathway® Polymer PY-PT42DE35 (formerly Tecophilic HP-60D-35) and cutting the extruded tubing into short segments that are the length of the eventual circumference of the finished VR101 devices. The tubing segments are filled with a solution of 87/10/3 (wt %) USP grade glycerol/USP grade water/USP grade sodium chloride solution. The ends of the tubing are subsequently thermally fused to form a continuous ring. The filled ring is placed into a mold and briefly heated in an annealing step to release stresses and form the ring into its final circular shape. The rings are packaged in foil-backed polyethylene pouches containing 0.25 mL of a glycerol/water solution.

Device dimensions are comparable to commercially available IVRs. Table 2 lists the dimensions of VR101.

J3 Bioscience, Inc.	Clinical Investigation Plan and Protocol CI03	CI03-CIP Rev. 02 Page 21 of 60
	A Clinical Investigation to Evaluate Efficacy of the J3 Bioscience Lubricating Intravaginal Ring VR101 as a Personal Lubricant Device in Women	

Table 2. Nominal Dimensions of VR101	
Ring Characteristic	Dimension
Outer Diameter (ring)	55 mm
Cross-Sectional Diameter (tubing)	5.50 mm
Wall thickness (tubing)	0.65 mm

Table 3 identifies composition and weight of VR101.

Table 3: Nominal Composition and Weight of VR101	
Device Component	Weight
Tubing (Pathway® PY-PT42DE35)	2.0 g
Lubricant Solution (Liquid Core)	2.5 g (total)
Glycerol, USP	2.2 g
Water, USP	0.2 g
Sodium Chloride, USP	0.1 g
Total Mass	4.5 g

Table 4 provides the specifications for VR101 constituents. VR101 does not contain any drugs or active pharmaceutical ingredients (APIs).

Table 4. Detailed Specifications for VR101 Constituents	
Ring	
Component	Material Description

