3.9 Sham Rings

To demonstrate that efficacy results from this study are clinically meaningful, lubricating/moisturizing effects not directly resulting from VR101 must be adequately controlled. Therefore, performance of VR101 will be compared that of a sham ring.

Sham rings will be manufactured identically to VR101, except:

- Tubing will be manufactured with Biomerics Quadraflex ALE-91A, an inert (non-hydrophilic) aliphatic polyether urethane. ALE-91A has identical manufacturer-reported flexural modulus (per ASTM D790) to Tecophilic HP-60D-35 (Pathway PY-PT42DE45), is non-hemolytic (per ASTM D756), is non-cytotoxic (per ISO 10993-5), and has been used to manufacture FDA-approved, long-term (>30 day) implantable medical devices.
- No lubricating solution will be added to the device lumen or the device package.

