5.1.2 Measures to Minimize Bias

- Participants will not have access to their previous responses, and thus, in any given FSFI survey participants will be unable to directly reference their previous responses.
- All participants, regardless of randomization status, will be presented with the same study materials, including device packaging and labeling, will undergo the same measurements, and will be presented with the same survey questions.

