
*If a participant does not elect to participate in the open-label extension, the follow-up will occur on day 35±2 instead of day 49±2. **Only if the participant elects to participate in the open-label extension ***Only if a participant decides to withdraw participation before reaching Day 26
							

J3 Bioscience, Inc.	Clinical Investigation Plan and Protocol CI03	CI03-CIP Rev. 02 Page 32 of 60
	A Clinical Investigation to Evaluate Efficacy of the J3 Bioscience Lubricating Intravaginal Ring VR101 as a Personal Lubricant Device in Women	

Visit 1 – Study Start / Randomization (Day 0)

1. Assign a Subject Number to the prospective participant and complete initial screening procedures.
2. Participants will be administered the FSFI survey (see Section 5.4.6) by a trained member of the study staff. Complete this as early as possible in the Visit, e.g., as soon as consent is obtained.
3. A staff member will conduct a Concomitant Therapy assessment, during which they will assess and record if any hormonal therapies are currently being used or have been used in the past 3 months (these may or may not disqualify the participant from enrollment, refer to Inclusion / Exclusion Criteria above). During this assessment, women still able to get pregnant will be asked about their current birth control method. If the method is allowed by inclusion / exclusion criteria (see above), they will be instructed to continue their same method. If no birth control is currently used, or their preferred method is to use condoms, they will be offered non-lubricated condoms as to allow them to participate in the study.
4. As part of the demographic assessment, participants will be queried as to their menopausal status. If a prospective participant is still able to get pregnant, she will be asked to provide a urine sample for a pregnancy test.
5. If participant meets all inclusion and exclusion criteria, they will be enrolled and given a numbered package of randomized study product. All packages will be identical in appearance and will contain 6 individually packaged study devices (either VR101 or sham ring). All packages will contain a unique number, which will be recorded by study staff.

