1. Participants will be asked to report any Adverse Events (AEs), and whether or not they feel the events were related to use of the investigational device. AEs will be recorded on the Adverse Event Form. Refer to Section 13 for further detail on classification of AEs and adverse device effects (ADEs).
2. If a participant is still able to get pregnant, she will be asked to provide a urine sample for a pregnancy test.
3. Participants will be administered the FSFI survey (see Section 5.4.6) by a trained member of the study staff.
4. A staff member will conduct a Concomitant Therapy assessment, during which they will determine the participant used any unapproved medication (e.g. change of dosing frequency of HRT / hormonal birth control).
5. Following the FSFI Survey, participants will be given the Intercourse / Lubricant Use Survey (see Section 5.4.7) to assess frequency of intercourse and assess if any unapproved lubrication sources were used.
6. Participants will be again queried as necessary to complete the Ring Use Log (see Section 5.4.8) up to all events that occur during Visit 2. If the participant does not continue in the open-label extension, then all information needed to fully complete all fields of her Ring Use Log should be collected during Visit 2.
7. Participants will be asked to return any unused devices to study staff.
8. A member of the study staff will ensure that all study devices are accounted for, i.e., that the number of unused devices returned is reconciled with reported ring use.
9. The participant will then be asked if she would like to participate in an open-label extension where she can use VR101 for 2 weeks (two devices, 1 week per device). Each participant will be instructed to discontinue use her final VR101 device at day 42 ± 2 and told she will receive a final follow-up call on day 49 ± 2.
10. If the participant would like to continue, a member of the study staff will provide her with two VR101 devices. Participants will be again shown to a private clinic area or restroom to remove her device and (if she has elected to continue) self-

J3 Bioscience, Inc.	Clinical Investigation Plan and Protocol CI03	CI03-CIP Rev. 02 Page 34 of 60
	A Clinical Investigation to Evaluate Efficacy of the J3 Bioscience Lubricating Intravaginal Ring VR101 as a Personal Lubricant Device in Women	

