insert one of the devices from the package. Participants will be asked to insert one of these rings per the instructions for use and without clinician input. However, the participant may elect to take the rings with her and insert later at her convenience. The participant should dispose of her used ring in the restroom wastebasket, used rings are not intended to be collected by study staff.

Early Termination Visit

1. If a participant withdraws consent during the study (before Day 26, attempt to schedule a Visit for the participant to return study products and disclose any Adverse Events or concomitant therapy changes. Refer to Section 13 for further detail on classification of AEs and adverse device effects (ADEs).
2. During this Visit, if appropriate, participants will be asked to provide a urine sample for a pregnancy test.
3. If consent has not been withdrawn prior to the Study Visit, participants will be administered the FSFI study, Intercourse / Lubricant Use Study, and queried as needed to complete the Ring Use survey (in that order).
4. The participant will be queried regarding the reason for her withdrawal and the response will be recorded on the Early Termination CRF, record as much detail as possible (e.g. lack of lubrication, too much lubrication, difficulty place/remove a ring, adverse event (related or unrelated to device), etc.)

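### The blinding measures do not cover the visible wet/dry difference between VR101 and sham, both final visits list adverse-event questions before the self-reported FSFI, and nothing visible checks whether blinding held

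*Protocol*

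**What the plan says.** **The two rings.** Protocol 3.1 fills the VR101 tubing with a glycerol, water and salt solution (2.5 g of the 4.5 g total in Table 3) and says of the pouch: "The rings are packaged in foil-backed polyethylene pouches containing 0.25 mL of a glycerol/water solution". Protocol 3.9 lists how the sham differs: "Tubing will be manufactured with Biomerics Quadraflex ALE-91A, an inert (non-hydrophilic) aliphatic polyether urethane", and "No lubricating solution will be added to the device lumen or the device package".

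**The blinding measures.** Protocol 5.1.2 says that all participants "will be presented with the same study materials, including device packaging and labeling". Protocol 5.3.5 makes the trial double-blind. Visit 1 in 5.4.3 has the numbered packages of six look alike, and 5.6 gives the sham the same labels and instructions. Exclusion criterion 20 keeps out women from earlier VR101 trials.

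**The order of questions.** At Visit 2, step 1 asks about adverse events and "whether or not they feel the events were related to use of the investigational device"; the FSFI is step 3. At the Early Termination visit, step 1 covers adverse events and therapy changes, and the FSFI again comes in step 3. At Visit 1 the instruction for the FSFI is: "Complete this as early as possible in the Visit".

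**The endpoint and its checks.** SAP 3.1 calls the FSFI a self-report survey and bases the only primary endpoint on its lubrication domain. SAP 9 lists three sensitivity analyses: other cut-offs, a curve-based analysis, and women who could not place the ring. None concerns blinding.

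**The concern.** Each woman opens about four pouches herself. Every pouch carries a label that names a lubricating ring and says it is meant to moisturize and lubricate (Protocol 3.6, 5.6 and Appendix B). A dry pouch holding a ring with an empty lumen is a cue to the sham arm, and it is there before the device can have any effect. The endpoint is her own rating of lubrication, the very property the cue suggests, and Protocol 5.1.3 confirms that no test equipment backs it up.

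Protocol 3.9 itself says that effects not directly due to VR101 must be adequately controlled, and the sham is the means of doing so. If some women infer their arm, expectancy can add to or imitate a device effect. Asking about adverse events and their cause just before the FSFI draws further attention to the device at the moment of scoring. With no record of what women believed, a positive result could not be defended on this ground, and a sceptical reader's doubt could not be settled either way.

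**Working it through.** **1. What matches between the arms and what does not**

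| Feature | VR101 | Sham | Same? |
|---|---|---|---|
| Outer package of six (5.4.3, Visit 1 step 5) | numbered package | looks identical | yes |
| Label and instructions (5.6) | VR101 text | same text | yes |
| Tubing (3.1, 3.9) | hydrophilic polyurethane | non-hydrophilic polyurethane, same reported flexural modulus | in part |
| Lumen (3.1 Table 3, 3.9) | 2.5 g solution | none | no |
| Pouch contents (3.1, 3.9) | 0.25 mL solution | none | no |

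So 5.1.2 is right about the outer package and labels, and wrong if read to include what is inside the pouch.

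**2. Order at the visits that supply a final score**

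| Step | Visit 2 | Early Termination |
|---|---|---|
| 1 | adverse events, plus her view of the cause | adverse events, therapy changes, product return |
| 2 | pregnancy test | pregnancy test |
| 3 | FSFI | FSFI (if consent stands), then lubricant survey, then ring query |
| Later | therapy (4), lubricant survey (5), ring log (6), open-label offer (9) | reason for withdrawal (4) |

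The two visits agree: adverse events first, FSFI third. Both feed the primary analysis: SAP Table 1 records a final score for all 9 of 175 early terminators (9/175 = 5.1%).

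**3. The plan's own sample size**

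Inputs from SAP 4.1: 30% versus 60%, two-sided alpha 0.01, power 0.90.

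n = [z(0.995)·√(2·p̄·(1−p̄)) + z(0.90)·√(p1(1−p1) + p2(1−p2))]² / (p2−p1)²

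With p̄ = 0.45: [2.576·√0.495 + 1.282·√0.45]² / 0.09 = (1.812 + 0.860)² / 0.09 ≈ 79.3, so 80 per arm (power at 80: 0.903). The stated figure reproduces. It says nothing about bias, but it fixes the arm size used below.

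**4. What a reporting shift would do (illustration)**

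From the documents: 80 per arm, 30% base rate, and the SAP 6.1 test Z = (p1−p2) / √[p1(1−p1)/n1 + p2(1−p2)/n2] at two-sided 0.05. Assumed: no true device effect, and a shift b in reported response towards VR101. The probability of a significant result favouring VR101 is the exact sum, over all i sham and j VR101 responders, of Bin(i; 80, 0.30) × Bin(j; 80, 0.30 + b) wherever Z ≥ 1.96. The last column splits the shift evenly: half up in VR101, half down in sham.

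| Shift b | All in the VR101 arm | Split between arms |
|---|---|---|
| 0 | 2.6% | 2.6% |
| 5 points | 10.4% | 10.4% |
| 10 points | 27.5% | 28.6% |
| 15 points | 51.5% | 55.4% |
| 20 points | 74.3% | 80.2% |

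Hand check at 10 points: SE = √[(0.21 + 0.24)/80] = 0.075; 0.10/0.075 = 1.333; P(Z > 1.960 − 1.333) ≈ 26.5%, close to the exact 27.5%.

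The smallest significant excess over 24/80 (30%) is 36/80 (45%): 0.15 / √[(0.21 + 0.2475)/80] = 0.15/0.0756 = 1.98. That is 15 points, half the 30-point difference planned in the SAP.

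**The case against.** **The plan does protect the blind.** A reader might infer that nothing limits expectancy. The documents do not support that: the measures listed above are real. The design is also parallel-group, so no woman handles both rings before the endpoint. Without a reference ring she may not read a dry pouch as sham, and what she was told at consent is not in the available text. This stands, and it is why the point is confined to the uncovered cue and the lack of measurement.

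**The visit order is consistent.** A reader might also infer that Visit 2 departs from the Early Termination visit. It does not, as the second table shows; only the question about cause is spelled out at Visit 2 alone. The Visit 1 instruction is a weak contrast, because there the FSFI decides eligibility before any ring is used. Adverse-event-first is also the natural reading of a numbered list rather than a stated rule; an explicit sequence is given at Visit 2 only for the lubricant survey.

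**Reordering gains little.** Adverse events are also asked about at the day 7, 14 and 21 calls, and both arms get the same questions. This stands in part: the change removes some of the cueing, not all.

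**The dry sham is deliberate.** Lubricant in the sham package could itself lubricate. This is a sound reason, so no change to the sham is proposed.

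**A guess is hard to interpret.** Wetness is the intended effect, so a late guess mixes benefit with unblinding. This stands, and it argues for an early guess with a reason, reported descriptively.

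**Conclusion.** The point holds in limited form. Three things are established from the documents: the pouch and ring contents differ visibly while 5.1.2 implies sameness; both visits that supply the final FSFI-LD list adverse events before it; and no visible text measures blinding, although the sole primary endpoint is self-reported. The last is judged on the available text, which lacks the consent form and parts of the SAP's blind-review section.

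A reader might infer from the percentages that the trial's false-positive rate is inflated by those amounts, or that the blind failed. Neither follows. The shifts of 5 to 20 points are assumptions; the documents contain nothing from which to estimate them. The figures show only that a modest shift would matter if it occurred.

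The weight depends on the result. A difference near the planned 30 points (SAP) or 34 points (protocol, 30% versus 64%) would not be explained by a shift of 5 to 15 points alone. A difference near the 15-point significance boundary could be. The changes are worth making because they are cheap, but the design is not invalid without them.

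**What to change.** 1. **Protocol 5.4.3:** make the FSFI the first assessment at both Visit 2 and the Early Termination visit (there, where consent has not been withdrawn), before the adverse-event, concomitant-therapy and ring questions. Changing Visit 2 alone would make the two sources of final scores differ. This adds no assessment and removes part of the cueing.
2. **Protocol 5.4.3 and 5.4.4, SAP 9:** add one question on which ring she thinks she has, with the reason (pouch or ring appearance, effect, other). Ask it soon after first insertion, for example at the day 7 call, and again right after the final FSFI and before the open-label offer. Tabulate the guess by arm and reason, descriptively only. The cost is one question asked twice and one table; the drawback is that asking draws some attention to allocation, equally in both arms.
3. **Protocol 5.1.2:** state that outer packaging and labels are identical but pouch contents differ, so that it agrees with 3.1 and 3.9.

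The device, sample size and primary test do not change. Protocol changes need sponsor and IRB approval under Protocol 10. SAP 10.1 records that data collection was complete when Rev. 00 was written. Where visits are already complete, changes 1 and 2 are no longer possible: make correction 3 and report in the clinical study report, as a limitation, that blinding was not measured.

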4 OBJECTIVES AND HYPOTHESES OF THE CLINICAL INVESTIGATION

4.1 Study Objectives (ECH E3; 8.)

4.1.1 Primary Objectives of the Clinical Investigation

To evaluate the efficacy of VR101 as a personal lubricant for vaginal application, intended to increase vaginal lubrication and enhance the ease and comfort of intimate sexual activity.

J3 Bioscience, Inc.	Clinical Investigation Plan and Protocol CI03	CI03-CIP Rev. 02 Page 24 of 60
	A Clinical Investigation to Evaluate Efficacy of the J3 Bioscience Lubricating Intravaginal Ring VR101 as a Personal Lubricant Device in Women	

4.2 Hypothesis of the Clinical Investigation

4.2.1 Primary Efficacy Hypothesis

Compared to the sham device, a significantly greater proportion of participants who use VR101 for 4 consecutive weeks will experience increased vaginal lubrication that enhances ease and comfort of intimate sexual activity as assessed by the Lubrication domain of the FSFI (FSFI-LD \geq 4.5).

4.3 Label Claims to be Assessed in the Clinical Investigation

Successful confirmation of the Primary Efficacy Hypothesis will also validate the following proposed VR101 Label Claims:

- Use one ring every 7 days to provide lubrication during sexual activity or intercourse
- Use one ring every 7 days to reduce discomfort during sexual activity or intercourse
- Use one ring every 7 days for increased comfort and lubrication
- Helps replenish vaginal lubrication when used once every 7 days
- Provides vaginal lubrication when used once every 7 days

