1.3 Summary of Endpoints (see Section 5.1.1 for details)

1.3.1 Primary Efficacy Endpoint

- Proportion of participants that experience increased vaginal lubrication that enhances ease and comfort of intimate sexual activity, defined as a FSFI-LD \geq 4.5 following 4 consecutive weeks of weekly ring use.

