5.1.1 Study Endpoints (ICH E9; 2.2.2)

- **Primary**: Proportion of participants that experience increased vaginal lubrication that enhances ease and comfort of intimate sexual activity, defined as an FSFI-LD \geq 4.5 with 4 consecutive weeks of weekly ring use.

J3 Bioscience, Inc.	Clinical Investigation Plan and Protocol CI03	CI03-CIP Rev. 02 Page 25 of 60
	A Clinical Investigation to Evaluate Efficacy of the J3 Bioscience Lubricating Intravaginal Ring VR101 as a Personal Lubricant Device in Women	

- **Exploratory:** Improvement in the Female Sexual Function Index (FSFI) total composite score (Rosen 2000) and its domains (Desire, Arousal, Lubrication, Orgasm, Satisfaction and Pain) during 28 days of use.
- **Safety endpoints monitored:**
 - Any adverse events and adverse device effects (ADE)

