6.3 Justification of Study Endpoints

6.3.1 FSFI-LD

As a personal lubricant device, VR101 is intended to supplement the body's natural lubrication to enhance the ease and comfort of intimate sexual activity. The Female Sexual Function Index (FSFI) is a survey validated to assess sexual function in women. The FSFI contains 19 questions, divided in to 6 characteristic domains: Desire, Arousal, Lubrication, Orgasm, Satisfaction, and Pain. Although all of these characteristics may be improved by use of a personal lubricant, only the Lubrication domain is directly relevant to a lubricant's intended use.

J3 Bio was asked by FDA to assess VR101 efficacy through analysis of individual improvement, rather than a comparison of group mean scores. Thus, we have proposed a threshold above which a participant's LD will be deemed resolved to a clinically meaningful degree and the participant considered to be a study "responder" (LD 4.5 out of 6). In the FSFI cross-validation study (Wiegel 2005) a lubrication sub score threshold of 4.35 out of 6 was noted as an accurate discriminant of overall sexual dysfunction. Since 4.5 is the next highest achievable score above 4.35, the primary efficacy hypothesis will be supported if the proportion of participants reaching a score of 4.5 or better following 4 weeks of VR101 use exceeds that following 4 weeks of sham ring use. Participants will only be enrolled in the study if they score 1, 2 or 3 (out of 5) on all 4 Lubrication Questions at baseline. The lower bound of 1 is justified because a score of 0 on any question would indicate that the prospective participant had not attempted intercourse in the past 3 months, which contradicts one of the key study inclusion criteria. For this study to yield reliable results, only participants that demonstrate a willingness to attempt intercourse should be enrolled. The upper bound of 3 is justified because a score of 3 or less represents a non-satisfactory response to each question as follows:

- Q7 and Q9: Lubrication "about half the time" or less during intercourse.

J3 Bioscience, Inc.	Clinical Investigation Plan and Protocol CI03	CI03-CIP Rev. 02 Page 38 of 60
	A Clinical Investigation to Evaluate Efficacy of the J3 Bioscience Lubricating Intravaginal Ring VR101 as a Personal Lubricant Device in Women	

- Q8 and Q10: Difficult, very difficult or extremely difficult to become/stay lubricated during intercourse.

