### 2.2 Hypotheses of the Clinical Investigation

Compared to the sham device, a significantly greater proportion of participants who use VR101 for 4 consecutive weeks will experience increased vaginal lubrication that enhances ease and comfort of intimate sexual activity as assessed by the Lubrication domain of the FSFI (FSFI-LD  $\geq$  4.5).

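### A primary win on FSFI-LD is said to validate a discomfort claim and a comfort claim, but none of the four scored items asks about comfort

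*Protocol*

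**What the plan says.** Protocol 4.3 sets the rule: "Successful confirmation of the Primary Efficacy Hypothesis will also validate the following proposed VR101 Label Claims". Five claims follow, with no further condition. The second is "Use one ring every 7 days to reduce discomfort during sexual activity or intercourse" and the third is "Use one ring every 7 days for increased comfort and lubrication". The other three concern lubrication alone.

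The primary endpoint is the proportion of participants with FSFI-LD of at least 4.5 after four weeks. Protocol 4.2.1 describes reaching that score as "increased vaginal lubrication that enhances ease and comfort of intimate sexual activity as assessed by the Lubrication domain of the FSFI". Protocol 1.3.1 and 5.1.1 and SAP 2.2 attach the same description to the same cut-off.

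Protocol 6.3.1 justifies the cut-off by a published finding: "a lubrication sub score threshold of 4.35 out of 6 was noted as an accurate discriminant of overall sexual dysfunction". The next achievable score, 4.5, was then chosen. The Pain domain (Q17 to Q19) is exploratory (Protocol 1.3.3 and 5.1.1, SAP 3.3), and SAP 6.2 plans no multiplicity adjustment for the exploratory analyses.

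**The concern.** A label claim validated by a trial should rest on something the trial's confirmatory test measures. Here two of the five claims speak of comfort or discomfort, while the confirmatory score is built only from lubrication items. The bridge is the endpoint's description, which declares that a score of 4.5 or more is lubrication of the kind that improves ease and comfort. That is a definition, not a measurement.

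The gap is more than formal, for three reasons.

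- Protocol 5.3.1 requires low scores on Q7 to Q10 but no discomfort at baseline, so women with no discomfort to reduce can enter and become responders.
- Protocol 13.2 and 13.3 list discomfort, coital problems and device-related pain among the anticipated events, so the plan itself allows that lubrication and comfort may move apart.
- The cut-off sensitivity analyses in SAP 9 move the FSFI-LD threshold to 4.2 and 4.8. None of the analyses there looks at comfort.

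The data are meant to support a 510(k) notification. Followed as written, 4.3 would report a lubrication result as validation of a discomfort claim.

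**Working it through.** **Inputs.** Item texts, domain factors and score ranges: Protocol Appendix A. Lubrication scoring: SAP 3.1. Eligibility (1, 2 or 3 on each of Q7 to Q10): Protocol 5.3.1. Claims: Protocol 4.3.

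**The plan's own scoring figures, reproduced.** FSFI-LD = 0.3 × (Q7 + Q8 + Q9 + Q10).

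- Lowest score with sexual activity: 0.3 × 4 = 1.2. Highest: 0.3 × 20 = 6.0. Both agree with SAP 3.1.
- 14 points give 0.3 × 14 = 4.2 and 15 points give 0.3 × 15 = 4.5, so 4.5 is indeed the first achievable score above 4.35.
- Highest eligible baseline: 0.3 × (3 + 3 + 3 + 3) = 3.6, so every participant starts below the threshold.

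**What the items ask.**

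| Item | Content | Domain | Comfort or discomfort? |
|---|---|---|---|
| Q7 | How often lubrication was achieved | Lubrication | No |
| Q8 | Difficulty of achieving it | Lubrication | No |
| Q9 | How often it was maintained | Lubrication | No |
| Q10 | Difficulty of maintaining it | Lubrication | No |
| Q17 | Frequency of discomfort or pain during penetration | Pain | Yes |
| Q18 | Frequency of discomfort or pain after penetration | Pain | Yes |
| Q19 | Level of discomfort or pain during or after penetration | Pain | Yes |

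So 0 of the 4 scored items ask about comfort. Of the 19 FSFI items, 3 ask about discomfort or pain, and all 3 are limited to vaginal penetration. Q8 and Q10 touch ease of lubrication, not ease or comfort of intercourse.

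**What the claims say.** 1 on discomfort only + 1 mixed + 3 on lubrication only = 5.

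**What the rule permits.** Pain = 0.4 × (Q17 + Q18 + Q19). With intercourse attempted it runs from 0.4 × 3 = 1.2 to 0.4 × 15 = 6.0. No Pain item enters FSFI-LD, so any Pain score in that range can occur with any responder pattern on Q7 to Q10. By enumeration, 122 of the 625 patterns scored 1 to 5 reach 15 points; this counts possibilities, not likelihoods. For example:

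- Q7 to Q10 move from 3, 3, 3, 3 to 4, 4, 4, 3: FSFI-LD goes from 3.6 to 0.3 × 15 = 4.5, a responder.
- In the same woman Q17 to Q19 move from 5, 5, 5 to 1, 1, 1: Pain goes from 6.0 to 1.2, a change of −4.8.

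She raises the responder proportion on which the discomfort claim rests. This shows what the rule allows; it is not a forecast. At trial level the same holds: the difference in responder proportions depends on Q7 to Q10 alone, so it can be significant whatever happens to Pain.

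**Evidence for the link in the documents.** Protocol 6.3.1 argues from intended use and from a cut-off for overall sexual dysfunction. Neither concerns discomfort. The CI02 diary result in Protocol 2.4.2 (88% favourable) concerns comfort of the ring during use, not discomfort in intercourse. SAP 4.1 states that VR101 had not been tested with FSFI-LD, so no earlier VR101 data on this score are available to supply the link.

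**The case against.** The strongest reply is that the link is reasoned, not merely verbal. Protocol 6.3.1 considers all six domains, says a lubricant may improve any of them, and selects Lubrication as the one directly relevant to intended use. SAP 3.1 adds that FDA supports the FSFI for evaluating VR101 efficacy. The cited FSFI papers, which this review could not consult, might relate lubrication to comfort. All this is rationale for choosing the instrument. None of it, as set out in the documents, shows that a score of 4.5 or more means less discomfort, and 4.3 speaks of validation. The limit on what could be read does stand: the finding is about what the documents contain.

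A second reply is that discomfort is measured anyway. Q17 to Q19 fit the intercourse part of the discomfort claim closely, because Appendix A defines intercourse as penile penetration. That is fair, though the claim also covers other sexual activity. The comparison remains exploratory and unadjusted, and the rule in 4.3 does not depend on it.

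A third is that a Pain test gated behind the primary could still be specified before unblinding. It could, but Protocol 8.6 provides for one tested hypothesis, and the documents give no Pain effect size or standard deviation. If the standardized difference is assumed to be 0.2, 0.3, 0.4 or 0.5, power at 80 per arm and two-sided 0.05 is Φ(d√(80/2) − 1.96) = 0.24, 0.48, 0.72 or 0.89. It is an option, not a ready substitute.

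Finally, the claims are only proposed, and the primary analysis is untouched. That limits the severity but does not make the rule right.

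**Conclusion.** The concern holds. Protocol 4.3 lets a test of lubrication validate one claim that is wholly about discomfort and one that is partly about comfort: 2 of 5 claims, with 0 of 4 scored items behind the comfort content. The conclusion rests on the item texts and scoring in Appendix A, and on the absence from the protocol and SAP of evidence relating FSFI-LD of 4.5 or more to discomfort. It makes no assumption about how strongly lubrication and discomfort are correlated in practice.

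The defect is confined to what the trial may conclude. The primary analysis, the pass/fail criterion in Protocol 8.5, the three lubrication-only claims and the lubrication half of the third claim are unaffected. It should be fixed.

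**What to change.** 1. **Protocol 4.3:** restrict the claims validated by the primary endpoint to lubrication. Remove the discomfort claim from the rule, and the reference to comfort from the third claim.
2. **Protocol 1.3.1 and 5.1.1:** define the endpoint as the proportion with increased vaginal lubrication (FSFI-LD ≥ 4.5) after four consecutive weeks of weekly ring use. **Protocol 4.2.1 and SAP 2.2:** delete the clause on ease and comfort. The intended-use wording in Protocol 3.3 and 4.1.1 and SAP 2.1 can stay as a statement of intent.
3. **Clinical study report:** carry the same limit.
4. **Pain domain:** report the planned between-arm comparison as exploratory evidence on discomfort or pain during or following vaginal penetration, not as validation of either claim.

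The cost is wording in four protocol sections and one SAP section, with sponsor and IRB approval for the protocol text under Protocol 10. No new data, test or alpha is needed. SAP 10.1 records that data collection is complete, so if the protocol is not reopened, stating the limit in the study report is enough. The price is that the discomfort and comfort claims lose the support of the primary result, and the exploratory Pain comparison cannot replace it as confirmatory evidence.
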